### **eDiary Zavegepant Sprays per Month Over Time**

eDiary zavegepant sprays per month over time are tabulated as a continuous variable at each month in the LTT analysis period for the safety analysis set. This analysis is based on absolute spray counts per month. Using the example above for exposure categories, the subject has 4, 3, 5, 6, and 0 sprays per month in Months 1 through 5, respectively, and 5 months in the LTT period as determined by calculating the ceiling([LTT end date – LTT start date + 1]/28).

This is also tabulated for the safety analysis set with  $\geq 51$  weeks in the LTT period.

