4.3 Schedule of Assessments

Table 1: Schedule of Assessments

		Г	Г		
Week 2 Follow-up Safety Visit (14 days after EOT visit +/- 2 days) ¹					X ₃
Weeks 8, 12, 16, 20, 24, 28, 32, 36, 40, 44, 48, 52 (or EoT) (all visits +/- 7 days) 7 days) 1					X
Week 4 (Day 29 +/- 2 days 1					×
$\frac{\text{Week 2}}{\text{(Day)}}$ $\frac{15}{+/-2 \text{ days)}^{1}}$					X
Baseline Visit (Day 1)		X			X
Visit (up to 5 days prior to Baseline Visit)					
Observation Phase (28 days +/- 2 days)					X
Screening Visit	X	X	X	X	X
Procedure	Informed Consent	Inclusion / Exclusion Criteria	Medical History	Migraine History (signs/symptoms/prior treatment/frequency/intensity)	Concomitant medication reported by subject in paper diary ²

¹ Every effort should be made to conduct the study visits within the specified windows. However, if necessary due to local COVID-19 safety requirements, visits may be performed outside of these windows in order to minimize any potential risks to subject safety and to comply with governmental and institutional

guidance. See sections 4.3.1 - 4.3.6 for more information.

² Concomitant medication, including migraine standard of care medication and prophylactic migraine medication, taken at any time during the study will be reported by subject on a medication log and reviewed by site staff at each study visit

³ Collect if treatment with concomitant medication is required for an AE or if concomitant medication is considered related to AE

Procedure	Screening Visit	Observation Phase (28 days +/- 2 days)	Visit (up to 5 days prior to Baseline Visit)	Baseline Visit (Day 1)	$\frac{\text{Week 2}}{\text{(Day)}}$ $\frac{15}{+/-2 \text{ days)}^{1}}$	Week 4 (Day 29 +/- 2 days 1	Weeks 8, 12, 16, 20, 24, 28, 32, 36, 40, 44, 48, 52 (or EoT) (all visits +/- 7 days)!	$\frac{\text{Week 2}}{\text{Eollow-up}}$ $\frac{\text{Safety}}{\text{Visit}}$ $\frac{\text{Uisit}}{\text{after}}$ $\frac{\text{after}}{\text{EOT}}$ $\frac{\text{visit } +/-2}{\text{days})^{1}}$
Physical Examination ⁴	X ₅		X			X	X (Weeks 24 and EoT only)	
Vital Signs/Physical Measurements ⁶	X		X		X	X	X	X
Nasal Inspection	X		X		X	X	X	X
Clinical Safety Laboratory Testing	X7		X			X	X (Weeks 24 and EoT only)	
Liver function tests (LFTs)	X_8		X		X	X	X	X
Lipid panel			X_{0}				X (Weeks 24 and EoT only)	
ECG	X^{10}					X	X (Weeks 24 and EoT only)	X
Urinalysis ¹¹			X				X (EoT only)	
Urine Drug Screen for drugs of abuse	×							

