- $\geq 6$  sprays per month for 1, 2, 3, 4, 5,  $\geq 12$ ,  $\geq 6$ ,  $\geq 3$  and  $\geq 1$  months
- $\geq 7$  sprays per month for 1, 2, 3, 4, 5,  $\geq 12$ ,  $\geq 6$ ,  $\geq 3$  and  $\geq 1$  months
- $\geq 8$  sprays per month for 1, 2, 3, 4, 5,  $\geq 12$ ,  $\geq 6$ ,  $\geq 3$  and  $\geq 1$  months.
- Total zavegepant exposure (sprays) summed across all subjects, derived by summing cumulative exposure across all subjects
- Total zavegepant exposure (patient-years), derived by summing (study drug end date – study drug start date + 1)/365.25 across all subjects.

See Section 7.1 for derived dates.

eDiary zavegepant and LTT exposure is also tabulated by subgroup level and overall for the safety analysis set for all subgroups of interest described in Section 4.3.

Months are 4-week (28-day) intervals in the LTT analysis period defined as follows:

- Month 1 ( $\leq 4$  weeks; study days 1 to 28)
- Month 2 ( $> 4$  to  $\leq 8$  weeks; study days 29 to 56)
- Month 3 ( $> 8$  to  $\leq 12$  weeks; study days 57 to 85)
- Month 4 ( $> 12$  to  $\leq 16$  weeks; study days 85 to 112)
- Month 5 ( $> 16$  to  $\leq 20$  weeks; study days 113 to 140)
- Month 6 ( $> 20$  to  $\leq 24$  weeks; study days 141 to 168)
- Month 7 ( $> 24$  to  $\leq 28$  weeks; study days 169 to 196)
- Month 8 ( $> 28$  to  $\leq 32$  weeks; study days 197 to 224)
- Month 9 ( $> 32$  to  $\leq 36$  weeks; study days 225 to 252)
- Month 10 ( $> 36$  to  $\leq 40$  weeks; study days 253 to 280)
- Month 11 ( $> 40$  to  $\leq 44$  weeks; study days 281 to 308)
- Month 12 ( $> 44$  to  $\leq 48$  weeks; study days 309 to 336)
- Month 13 ( $> 48$  to  $\leq 52$  weeks; study days 337 to 364)
- Month 14 ( $> 52$  to  $\leq 56$  weeks; study days 365 to 392).

See Section 7.3 for the definition of study days.

Exposure categories assess the number of months in which a subject exceeded select spray counts in the LTT analysis period (see Section 7.2), where the number of months are not necessarily consecutive. For example, suppose a subject administers 4 sprays in Month 1, 3 sprays in Month 2, 5 sprays in Month 3, 6 sprays in Month 4, and 0 sprays in Month 5. Thus, this

subject is considered to have administered  $\geq 2$  sprays per month for 4 months (i.e., Months 1 through 4),  $\geq 4$  sprays per month for 3 months (i.e., Months 1, 3 and 4), and  $\geq 6$  sprays per month for 1 month (i.e., Month 4).

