##### **6.4.6.1 Migraine Days per Month over Time**

Tables present results separately for the (1) migraine analysis set, and (2) migraine analysis set taking concomitant prophylactic migraine medication (see Section 6.2.5.2).

The number of migraine days per month in the LTT period is examined relative to the number of migraine days per month in the OP by migraine intensity (total [mild, moderate, severe, unable to recall, not reported]; moderate or severe). The following tables are produced:

- Values and changes (both absolute and percent) from the OP in the number of migraine days per month by month during LTT and in the overall LTT summarized descriptively as continuous variables by migraine intensity (including 2-sided 95% normal CIs for mean

change). The number of migraine days per month are prorated to 28 days and derived as follows:

- OP:  $28 \times (\text{total number of migraine days in the OP analysis period}) / (\text{total number of data days in the OP analysis period})$ .
- Month during LTT:  $28 \times (\text{total number of migraine days in the month}) / (\text{total number of data days in the month})$ . In addition, subjects must have  $\geq 14$  days of data (not necessarily consecutive) in a month to be evaluable for that month.
- Overall LTT:  $28 \times (\text{total number of migraine days in the LTT analysis period}) / (\text{total number of data days in the LTT analysis period})$ .
- Number and percentage of subjects with  $\leq 0\%$ ,  $\geq 25\%$ ,  $\geq 50\%$ ,  $\geq 75\%$ , and  $100\%$  reduction from the OP in the number of migraine days per month by month during LTT and during overall LTT by migraine intensity.

The following plots are produced for the migraine analysis set:

- Scatter plot of change from OP in the number of total migraine days per month in the overall LTT on the y-axis versus number of total migraine days per month in the OP on the x-axis
- Scatter plot of percent change from OP in the number of total migraine days per month in the overall LTT on the y-axis versus number of total migraine days per month in the OP on the x-axis
- Scatter plot of change from OP in the number of moderate or severe migraine days per month in the overall LTT on the y-axis versus number of moderate or severe migraine days per month in the OP on the x-axis

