### 7.3 Analysis Visit Windows

Refer to Protocol Section 4.3 for the schedule of assessments.

Study days are calculated from the LTT start date as follows:

- Measurement date – LTT start date + 1, if measurement date  $\geq$  LTT start date
- Measurement date – LTT start date, if measurement date  $<$  LTT start date.

Treatment days are calculated from the study drug start date as follows:

- Measurement date – study drug start date + 1, if measurement date  $\geq$  study drug start date
- Measurement date – study drug date, if measurement date  $<$  study drug start date.

Follow-up days are calculated from the LTT last date as follows:

- Measurement date – LTT last date, if measurement date  $\geq$  LTT last date + 1
- Measurement date – LTT last date – 1, if measurement date  $<$  LTT last date + 1

Evaluation intervals are based on study days in the LTT analysis period and follow-up days in the follow-up analysis period (see Section 7.2). Table 3 presents analysis visit windows.

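### The sprays-per-month-over-time table enters partial last months as full months, so Month 14 shows an artificial fall for completers seen on or after Day 365

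*SAP*

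**What the plan says.** SAP 6.2.6.1 summarises sprays per month as a continuous variable, month by month, for the safety analysis set, and repeats the table for subjects with at least 51 weeks in the LTT period. On the metric it says: "This analysis is based on absolute spray counts per month". Its worked example credits a subject with "5 months in the LTT period as determined by calculating the ceiling([LTT end date – LTT start date + 1]/28"), so an incomplete last month counts as a month. Month 13 is "study days 337 to 364" and Month 14 is "study days 365 to 392".

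The paragraph states no minimum number of days and no proration. SAP 9.2, describing nasal medication deviations, confirms that drug exposure results are not prorated to 28 days. Under SAP 6.2.6, a day without drug data counts as a day without dosing.

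Two other by-month derivations treat short months differently. SAP 6.4.6.1 (migraine days) prorates to 28 days and requires at least 14 "days of data (not necessarily consecutive) in a month to be evaluable for that month". SAP 6.4.6.2 (treated migraine days) prorates months with at least 14 study days and keeps the raw count for shorter ones.

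**The concern.** This table shows whether monthly use was sustained over the year. A raw count from a month observed for one day is not comparable with a count from 28 days, yet both enter the same kind of column summary. If the final visit routinely falls just past a month boundary, the last column holds mostly fragments, and steady use looks like a sharp drop at the end. A reader could take that as loss of use or loss of benefit when only the calendar caused it. A displayed number of subjects would not reveal how many days each was observed.

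**Working it through.** **Inputs**
- Study-day origin, SAP 7.3: "Study days are calculated from the LTT start date as follows", with Day 1 the LTT start date.
- Visit convention, Protocol Table 1: Week 2 is Day 15 and "Week 4 (Day 29 +/- 2 days"), so Week w is Day 7w + 1.
- Week 52 visit window: ±7 days (Protocol synopsis and Table 1).
- LTT end, SAP 7.1: the later of the last complete eDiary finding date and the last visit date through Week 52 or early termination.
- Rates of use: constant at 2, 4 or 8 sprays per 28 days. This is an assumption. The ends of the range are the infrequent-use threshold in Protocol 6.6 and the maximum in Protocol 7.2.2.

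**Reproducing the plan's figures.** If Month k runs from Day 28(k − 1) + 1 to Day 28k, Month 13 is Days 337 to 364 and Month 14 is Days 365 to 392, as listed. Thirteen of the 14 listed months agree. Month 3 is listed as Days 57 to 85 where the rule gives 57 to 84, so Day 85 sits in two months; that is a separate slip. The example's five months follows for any LTT length of 113 to 140 days.

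**Where Week 52 falls.** 7 × 52 + 1 = Day 365. The target-day column of SAP Table 3 is blank in the text available for this review, so this day is derived. The Table 3 window for Week 52, Days 351 to 378, has midpoint 364.5 and agrees with it. Then ceiling(365/28) = ceiling(13.04) = 14, with 365 − 364 = 1 day in Month 14.

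**Size.** Expected last-month count = rate × (days in last month)/28.

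| LTT end | Months | Days in last month | Count at 2 / 4 / 8 per 28 days | Shortfall |
|---|---|---|---|---|
| Day 358 | 13 | 22 | 1.57 / 3.14 / 6.29 | 21.4% |
| Day 364 | 13 | 28 | 2 / 4 / 8 | 0% |
| Day 365 | 14 | 1 | 0.07 / 0.14 / 0.29 | 96.4% |
| Day 366 | 14 | 2 | 0.14 / 0.29 / 0.57 | 92.9% |
| Day 372 | 14 | 8 | 0.57 / 1.14 / 2.29 | 71.4% |

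The percentage shortfall does not depend on the rate.

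**Visits spread evenly over Days 358 to 372 (assumption).** 8 of 15 days, or 53%, give a Month 14. Its mean length is (1 + 2 + … + 8)/8 = 4.5 days, a shortfall of 1 − 4.5/28 = 84%. Month 13 averages (175 + 8 × 28)/15 = 26.6 days, about 5% low.

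**Subjects with at least 51 weeks.** 51 × 7 = 357 days. Months 1 to 12 end on Day 336 and are complete; Month 13 has at least 357 − 336 = 21 days. Month 14 is as short as in the main table.

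**Interim report.** SAP 8 excludes only the migraine-set, migraine-days and one subgroup outputs, so this table is produced. Each ongoing subject's last month is cut at the data cut. If cuts fall evenly within a month (assumption), that month averages 14.5 of 28 days, about 48% low for those subjects. The effect on a column depends on how many subjects are cut there, which the documents do not give.

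**The case against.** The strongest reply is that unprorated counts were chosen on purpose. The SAP revision history for Version 5.0 records that this analysis was specified as absolute counts, with an example, and SAP 9.2 shows this is the exposure convention. The protocol's limit on use is itself a count per 28 days. Month 14 lies beyond 52 weeks, so residual days are expected there. The table is descriptive, efficacy is not assessed, average sprays per month is divided by time in LTT once that reaches two weeks, and cumulative exposure is untouched.

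All of that stands and limits the point. It does not make a mean over fragments of one to eight days comparable with a mean over 28-day months.

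Two stronger readings are tempting. A reader might infer that the 51-week table is no help because it holds the same subjects. It does help: early discontinuers' partial months are gone and Months 1 to 12 are complete. A reader might also infer that the SAP guards against short months everywhere else. Only SAP 6.4.6.1 excludes them; SAP 6.4.6.2 keeps their raw counts, and the exposure categories state no minimum either.

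The Zavegepant Core SAP is not among the documents. SAP 6.1.2 refers to it for descriptive statistics, but the paragraph on this table does not refer to it for any rule on short months.

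**Conclusion.** The concern holds, mainly for Month 14. With LTT ending on Days 365 to 372 and a constant rate of use, the Month 14 count is 71% to 96% too low, or 84% on average under evenly spread visits. Month 13 is then about 5% low. In the full safety-set table, partial last months of early discontinuers, and of ongoing subjects at the interim, also lower earlier columns; the documents do not allow that effect to be sized overall.

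The figures rest on the derived Day 365. A later diary entry, or an end-of-treatment visit delayed for COVID-19 as Protocol 4.3.5 allows, would lengthen Month 14 and shrink the shortfall. LTT ending on Day 364 or earlier produces no Month 14.

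A reader might infer that the exposure results as a whole are unreliable. The documents do not support that: average and cumulative exposure, the exposure categories and the check for more than 8 sprays in a month are outside this point. The change should be made because a reported trend would otherwise mislead; no primary result depends on it.

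**What to change.** In the by-month table only, include a subject-month if it has at least 14 study days in the LTT period, and prorate its count to 28 days. The threshold is that of SAP 6.4.6.1, applied to study days instead of days of diary data. Exclude shorter subject-months; do not keep their raw counts as SAP 6.4.6.2 does. The exclusion is essential: with proration alone, one spray in a one-day Month 14 would become 28 × 1/1 = 28 per month.

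Under this rule Month 14 keeps only subjects whose LTT ends on Day 378 or later (378 − 364 = 14), and a Month 13 of 22 to 28 days prorates back to the underlying rate.

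If absolute counts are preferred, restrict the table to complete 28-day subject-months and do not summarise Month 14. Either way, keep the absolute counts in the by-subject listing and leave the other exposure outputs as they are.

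The cost is one sentence in the SAP, a small programming change, and a few partial months leaving the table.

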### **eDiary Time on Zavegepant and in LTT**

Kaplan-Meier mortality tables summarize time on zavegepant and time in the LTT period in 4-week intervals (i.e.,  $\leq 4$ ,  $> 4$  to  $\leq 8$ , ...,  $> 52$ ) for the safety analysis set. A Kaplan-Meier mortality plot displays the percentage of subjects in the LTT period (y-axis) versus weeks (x-axis). Subjects with non-missing response to the question “Did the subject complete the study?” on the Study Exit Status CRF are considered to have discontinued both zavegepant and the LTT period; otherwise, in an interim analysis, subjects are censored at the study drug end date or the LTT end date, respectively.

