#### 6.2.3.3 *Subject Disposition from Treatment through Follow-up*

Subject disposition from treatment through follow-up is tabulated for the safety analysis set as the number and percentage of subjects in the following categories:

- Ongoing in the study (identified as those with missing response to the question “Did the subject complete the study (including the follow-up visit)?”). This category only exists before the final database lock. After the final database lock, subjects with missing response are categorized as “Did not complete the study”.
- Completed the study (identified as those with “yes” response to the question “Did the subject complete the study (including the follow-up visit)?”)
- Did not complete the study (identified as those with “no” response to the question “Did the subject complete the study (including the follow-up visit)?”)
  - Reasons for early discontinuation, including not reported
- Terminated the study prematurely due to COVID-19 (see Section 9.1.4)
  - Reasons for premature termination, including not reported.

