### **eDiary Zavegepant and LTT Exposure**

eDiary zavegepant and LTT exposure is tabulated as continuous or categorical variables for the safety analysis set, and includes the following parameters:

- Time in the OP (weeks), derived as  $(OP\ end\ date - OP\ start\ date + 1)/7$
- Time from LTT start to last contact (weeks), derived as  $(last\ contact\ date - LTT\ start\ date + 1)/7$
- Time in the LTT period (weeks), derived as  $(LT\ end\ date - LT\ start\ date + 1)/7$
- Time in the LTT period (weeks) categories:  $\geq 11$ ,  $\geq 23$ ,  $\geq 51$ . These correspond to using a 1-week lower bound on 3, 6, and 12 months, respectively.
- Time on zavegepant (weeks), derived as  $(study\ drug\ end\ date - study\ drug\ start\ date + 1)/7$
- Time on zavegepant (weeks) categories:  $<12$ ,  $\geq 12$  to  $< 24$ ,  $\geq 24$  to  $< 36$ ,  $\geq 36$  to  $< 48$ ,  $\geq 48$ . These align with subgroups specified in Section 4.3.
- Cumulative zavegepant exposure (sprays), derived by summing number of sprays across records with complete study drug dates
- Cumulative zavegepant exposure (sprays) categories:  $< 20$ ,  $\geq 20$  to  $< 40$ ,  $\geq 40$  to  $< 60$ ,  $\geq 60$  to  $< 80$ ,  $\geq 80$ . These align with subgroups specified in Section 4.3.
- Average zavegepant exposure (sprays per month), derived as (1) cumulative zavegepant exposure (sprays) if time in the LTT period  $< 2$  weeks, or (2)  $4 \times$  cumulative zavegepant exposure/time in the LTT period if time in the LTT period  $\geq 2$  weeks.
- Average zavegepant exposure (sprays per month) categories:  $< 6$ ,  $\geq 6$ . These align with subgroups specified in Section 4.3.
- Number and percentage of subjects who administered  $> 1$  spray on any 1 day
- Number and percentage of subjects who administered  $> 8$  sprays per month in any month
- Exposure categories, defined as the number and percentage of subjects who administered
  - $\geq 1$  spray per month for 1, 2, 3, 4, 5,  $\geq 12$ ,  $\geq 6$ ,  $\geq 3$  and  $\geq 1$  months
  - $\geq 2$  sprays per month for 1, 2, 3, 4, 5,  $\geq 12$ ,  $\geq 6$ ,  $\geq 3$  and  $\geq 1$  months
  - $\geq 3$  sprays per month for 1, 2, 3, 4, 5,  $\geq 12$ ,  $\geq 6$ ,  $\geq 3$  and  $\geq 1$  months

- $\geq 4$  sprays per month for 1, 2, 3, 4, 5,  $\geq 12$ ,  $\geq 6$ ,  $\geq 3$  and  $\geq 1$  months
- $\geq 5$  sprays per month for 1, 2, 3, 4, 5,  $\geq 12$ ,  $\geq 6$ ,  $\geq 3$  and  $\geq 1$  months

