## **7 CONVENTIONS**

### **7.1 Derived Dates**

Derived dates for defining analysis periods are defined as follows:

- Study drug date/time: Complete finding date/time corresponding to “yes” response to question about taking study medication and number of sprays  $> 0$  in the eDiary evening report or medication reconciliation form.
- Study drug start date/time: Earliest study drug date/time.
- Study drug end date/time: Latest study drug date/time.
- Study drug last date/time: Study drug end date/time derived only for subjects with non-missing response to the question “Did the subject complete the study?” on the Study Exit Status CRF. Thus, in an interim analysis, all post-baseline data are included for a subject who is still on study. At the last database lock, the study drug last date is equal to the study drug end date.
- LTT start date/time: Earlier of (1) study drug start date/time, and (2) IWRS baseline visit date (i.e., Baseline/Day 1 visit date from the BHV3500\_202 IWRS Visit Report csv file).
- LTT end date/time: Later of (1) latest complete finding date/time in the eDiary on or after the LTT start date/time, and (2) latest complete visit date on or after the LTT start date through the Week 52/Early Termination visit date, and excluding the Follow-up Week 2 visit date, from the Visit Date CRFs.

- LTT last date/time: LTT end date/time derived only for subjects with non-missing response to the question “Did the subject complete the study?” on the Study Exit Status CRF. Thus, in an interim analysis, all LTT data are included for a subject who is still on study. At the last database lock, the LTT last date is equal to the LTT end date.
- OP start date/time: Earliest complete finding date/time in the eDiary before the LTT start date/time.
- OP end date/time: Latest complete finding date/time in the eDiary before the LTT start date/time.
- COVID-19 visit date: (1) Complete visit date, if it exists; (2) otherwise, complete date the visit was planned to occur for a missed visit (see Section 9.1.1).

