## 8 CONTENT OF REPORTS

An interim CSR is produced to support the intranasal zavegepant new drug application submission. All TLFs described in this SAP are produced for the interim CSR, except those for the migraine analysis set, exploratory endpoint of migraine days per month, and the subgroup of total treated migraine days per month in the overall LTT (see Sections 4.1, 4.3, and 6.4.6).

The final CSR is produced after the final data base lock, which occurs after the last subject reaches Follow-up Week 2. All TLFs described in this SAP are produced for the final CSR.

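### Does counting completers as events make the Kaplan-Meier outputs for time in LTT and time on zavegepant wrong at the final lock?

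*SAP*

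**What the plan says.** The rule is in SAP 6.2.6.1, under eDiary Time on Zavegepant and in LTT. Kaplan-Meier tables in 4-week intervals are planned for both durations in the safety analysis set, with one figure: "A Kaplan-Meier mortality plot displays the percentage of subjects in the LTT period (y-axis) versus weeks (x-axis"). Subjects with a non-missing answer to the completion question on the Study Exit Status form "are considered to have discontinued both zavegepant and the LTT period". For the rest, "otherwise, in an interim analysis, subjects are censored at the study drug end date or the LTT end date, respectively".

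Four other places bear on this:

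- SAP 6.2.3.3 identifies a completer by a yes to "Did the subject complete the study (including the follow-up visit")? It also deals with unanswered forms: "After the final database lock, subjects with missing response are categorized as" not having completed.
- SAP 7.1 sets the end of drug time at the last spray: "Study drug end date/time: Latest study drug date/time". It uses the same exit answer to create the *last dates*, and says that these equal the *end dates* at the last lock.
- SAP 6.2.6.1 tabulates time in LTT at 11, 23 and 51 weeks or more: "These correspond to using a 1-week lower bound on 3, 6, and 12 months, respectively".
- SAP 8 places these outputs in an early report as well: "An interim CSR is produced to support the intranasal zavegepant new drug application submission".

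**The concern.** Many readers take a Kaplan-Meier curve with discontinuation as its event to show how many subjects stay on treatment. Under that reading a completer should be censored at the planned end, not counted as a failure. The SAP does the opposite and gives no censoring rule for the final lock, so the curve must reach zero even in a trial with perfect retention.

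The drug-time table looks worse. Zavegepant is taken as needed, so a completer's event falls on the last spray, which may come weeks before the Week 52 visit. Late rows could look like subjects abandoning the drug when they simply had no further attack to treat. The section also does not say what happens to a subject whose exit answer is still missing at the final lock.

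At stake would be a wrong impression of long-term tolerability in the final report and, if the data cut is late enough, in the interim report for the marketing application.

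**Working it through.** The documents state no Kaplan-Meier value, so there is no planned figure to reproduce. The check compares the planned rule (all exits are events) with the alternative (Week 52 completers censored). Dropout, visit spread and spray pattern are assumptions.

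**Time in LTT.** Inputs: the end-of-treatment visit is at Week 52 ± 7 days (Protocol synopsis and Table 1). Time is (LTT end − LTT start + 1)/7, so 52 weeks is day 364. LTT end is taken as the visit date, with no later diary entry. With everyone an event, the estimate is one minus the empirical distribution:

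S(52) = (1 − dropout) × P(end-of-treatment day > 364).

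- Visits even over days 358–372 (Week 52 = Day 365): P = 8/15 = 53%.
- Visits even over days 357–371 (Week 52 = Day 364): P = 7/15 = 47%.
- COVID-19 delays, visits even over days 358–393: P = 29/36 = 81%.

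| Dropout | Planned rule, Week 52 (P = 47% to 53%) | Completers censored |
|---|---|---|
| 0% | 47–53% | 100% |
| 20% | 37–43% | about 80% |
| 30% | 33–37% | about 70% |
| 50% | 23–27% | about 50% |

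In the delayed-visit case with 30% dropout, the planned rule gives 0.7 × 29/36 = 56%. With the standard window the curve reaches 0% at 372/7 = 53.1 weeks. The earliest planned completion is 358/7 = 51.1 weeks (51.0 if Week 52 is Day 364), so the two rules agree up to about Week 51.

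**Time on zavegepant.** Simulation of 200,000 subjects: 30% dropout at a constant hazard, visits even over days 358–372, randomly spaced sprays, time = last spray − first spray + 1.

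| Sprays per 28 days | Week 48, planned | Week 48, censored | Week 52, planned | Week 52, censored |
|---|---|---|---|---|
| 2 | 46% | 71–72% | 2% | 69–70% |
| 4 | 67% | 71–72% | 7% | 70% |
| 8 | 72% | 72% | 17% | 70% |

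With evenly spaced sprays the planned Week 48 values are 71, 72 and 72%, and the Week 52 values are 3, 11 and 26%. The large Week 48 gap therefore needs both infrequent use and random timing. Protocol 6.6 removes subjects averaging fewer than 2 doses per month over 3 consecutive months, which limits the low end.

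The planned Week 52 values are also the shares still at risk under the alternative. Of 600 subjects they are 0.02 × 600 = 12, 0.07 × 600 = 42 and 0.17 × 600 = 102. The 70% comparator would rest on those few.

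**Interim report.** With accrual even over 5 months and 30% dropout, a cut 365 days after the first Day 1 shows no effect. Cuts at days 420 to 480 give 45 to 41% at Week 52, against 72 to 71% with completers censored.

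**The case for a change.** The strongest case for a change is that the SAP chose the word *discontinued*. Elsewhere it separates completing from discontinuing early (2.1 and 6.2.3.3), and here it merges them. A reader who sees 37% at Week 52 may not realise that the retention figure is near 70%. The Core SAP, to which 6.1.1.1 refers for Kaplan-Meier details, is not among the documents and cannot be relied on to correct an explicit rule. All of this stands as a remark on wording.

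It does not stand as a fault in the analysis. The output belongs to the Exposure section, its tables summarise time in a period, and its axis shows the percentage of subjects in that period. After the last end-of-treatment visit nobody is in the period, so 0% is the correct value. A curve held at 70% would contradict its own axis.

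No final-lock censoring rule is needed either. That lock follows the last subject's follow-up visit, so every duration is fully observed. At an interim cut, censoring only ongoing subjects is the usual treatment of incomplete durations.

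The SAP also uses the word in the same loose way in 6.2.6.2, where anyone with a study drug last date counts as having discontinued the study. A missing exit answer at the final lock is a small gap. SAP 6.2.3.3 already treats such subjects as not having completed, and a programmer would count their period as ended.

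**Conclusion.** The reading of the text is right: completers are events, and both outputs reach 0% after Week 52. No change to the plan follows, because these are distributions of exposure duration and the rule is coherent for that purpose at the interim and final locks.

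Censoring completers would leave the time-in-LTT values at Weeks 12, 24, 36 and 48 as they are and alter only the part beyond about Week 51. It would also make the drug-time estimate at Week 52 depend on roughly 2 to 17% of subjects. Retention is already available from the disposition table, with reasons, and from the category of 51 weeks or more in LTT. No primary endpoint or safety conclusion depends on the Kaplan-Meier outputs.

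The Week 52 differences (for example 33 to 37% against 70%) rest on assumed dropout and an even spread of visits. The drug-time figures also depend on the assumed spray pattern. The conclusion does not depend on them, since it follows from what the outputs are built to measure. What remains is loose wording: *ended* would have been a better word than *discontinued*.
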